#### 7.1.2 Serious Adverse Event (SAE) Reporting to Sponsor and IRB/EC

If the AE meets any of the criteria below, it is regarded as a serious adverse event (SAE).

- a) Led to a death,
- b) Led to a serious deterioration in health of the subject, that either resulted in
  1. a life-threatening illness or injury, or
  2. a permanent impairment of a body structure or a body function, or
  3. in-patient hospitalization or prolongation of existing hospitalization, or

## Clinical Investigation Plan

- 4. medical or surgical intervention to prevent life threatening illness or injury or permanent impairment to a body structure or a body function.
  - 5. chronic disease
- c) Led to fetal distress, fetal death or a congenital abnormality or birth defect.

**Note:** A planned hospitalization for pre-existing condition, or a procedure required by the CIP, without a serious deterioration in health, is not considered to be an SAE.

Study site representative will report all SAEs on a Case Report Form (CRF) in the database . When the system is down for more than 24 hours, sites will be directed to utilize the Clinical Adverse Event case report form (CRF) for Adverse Event (AE) and send to the Sponsor via email at [REDACTED]

### 7.1.2.1 SAE Reporting

The investigator should report all SAEs to the Sponsor as soon as possible but no later than outlined below.

Clinical Site	Reporting timelines
All Sites	SAEs must be reported to the Sponsor no later than 3 calendar days from the day the site personnel became aware of the event or as per the investigative site's local requirements, if the requirement is more stringent than those outlined.

The date the site staff became aware the event met the criteria of an SAE must be recorded in the source document. The Investigator will further report the SAE to the local IRB/EC according to the institution's IRB/EC reporting requirements.

### 7.1.3 Adverse Event Reporting to Country Regulatory Authorities by the Sponsor

The Sponsor will report SAEs and reportable device deficiencies/malfunctions to the country regulatory authority, per local requirements.

### 7.1.4 Independent Adjudication of Adverse Events

Independent review and adjudication of pre-specified events reported by investigators or identified by Safety personnel for the clinical investigation will be performed by qualified physicians not participating in the PerAF APAC trial as defined in the charter and according to definitions provided in this CIP, which will be used for assessment of the safety secondary endpoint.

## 8.0 STATISTICAL CONSIDERATIONS

The following section describes the statistical methods for the clinical investigation.

[REDACTED]

[REDACTED]

[REDACTED]

[REDACTED]

[REDACTED]

## Clinical Investigation Plan

### 8.2 Statistical Analyses

The primary endpoints and additional evaluation analyses will be summarized descriptively based on available data or measurements in the analysis population. No formal hypothesis testing will be performed.

#### 8.2.1 Primary Safety Endpoint Analysis

The primary safety endpoint will be summarized as the percentage of subjects who experienced one or more primary safety endpoints. The primary safety analysis population for the primary safety endpoint will be subjects in the primary analysis population who have completed their 7-day follow-up visit; or crossed the end of the 7-day visit window without the visit but with a primary safety endpoint event. Subjects without an event that are lost to follow up without a visit at or beyond their 7-day follow up visit window will be excluded from this analysis.

The primary safety endpoint event rate will be calculated based on the number of subjects experiencing a primary safety endpoint event divided by the total number of subjects in the analysis population. Relatedness of the event to the catheter and to the procedure will be determined by the independent physician reviewer.

#### 8.2.2 Additional Data Analyses

Additional data to be collected in this clinical investigation are described and will be reported using summary statistics. No hypothesis tests will be performed.

In general, continuous (CONT) variables will be summarized with the numbers of observations, means with standard deviations, quartiles, minimums, maximums as per the table mockups.

Categorical (CAT) variables will be summarized with subject counts and percentages/rates, and where specified in the table mockups.

Survival (SURV) analysis will be conducted to analyze time-to-event variables. Subjects without events will be censored at their last known event-free time point. Subjects withdrawn or otherwise lost to follow-up during the follow-up period will be censored at their last known visit. Survival data will be presented using the Kaplan-Meier product limit method.

The following list of analyses describes how the additional evaluations will be analyzed:

- Acute procedural success, defined as confirmation of entrance block in all pulmonary veins (CAT)
- Proportion of subjects off all Class I or III AADs taken to treat AF/AFL/AT at 15-months (SURV)
- Proportion of subjects who achieve 15-month single procedure success, defined as freedom from documented AF/AFL/AT recurrence (episodes >30 seconds) during the 9-month period following the blanking and therapy consolidation periods after a single ablation procedure (SURV)
- 
- Changes in EQ-5D-5L scores from baseline to follow-up at 3, 6, 12, and 15-months after the initial procedure (CONT)

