### 5.3.2 Inclusion Criteria

- 1) Patient must provide written informed consent prior to any clinical investigation related procedure.
- 2) Documented symptomatic persistent AF, which is defined as continuous AF sustained beyond 7-days and less than 1-year that is documented by (1) a physician's note AND (2) a 24-hour Holter within 90-days prior to the procedure, showing continuous AF, OR (3) two electrocardiograms (from any form of rhythm monitoring) showing continuous AF, with electrocardiograms taken at least 7 days apart
- 3) Refractory or intolerant to at least one Class I or III antiarrhythmic drug (AAD) as evidenced by recurrent symptomatic AF  
Note: Intolerance is defined as unable, unwilling, or refusal to take Class I or III AADs.
- 4) Age 18 years or older
- 5) Able and willing to comply with all pre-, post-, and follow-up testing and requirements

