## Clinical Investigation Plan

the ablation strategy is left to the discretion of the investigator, other than the requirement for PV isolation, this clinical investigation will not require that all subjects discontinue Class I and III AADs for at least five half-lives. However, AAD usage (start and stop date, time, frequency and dose information) will be documented for the trial prior to and after the subject's procedure(s).

During the blanking period after the ablation procedure, it is recommended that any current AAD medication be continued following the ablation procedure to aid with healing. Current AADs should be withdrawn 4-6 weeks after ablation, unless clinically contraindicated, to assess for recurrence of symptoms and for determination of the need for a repeat ablation during the blanking or therapy consolidation periods. It is recommended that sites phone subjects 4-6 weeks after ablation to remind them to discontinue their AAD medication.

It is recommended that subjects be taken off all Class I and III AADs prescribed for AF/AFL/AT after the blanking and therapy consolidation periods. If the investigator feels that the subject may benefit from a Class I or III AAD during the 9-month evaluation period (post-blanking and therapy consolidation periods), then the investigator should first prescribe a previously ineffective Class I or III AAD up to the historic maximum ineffective dose prior to the ablation procedure. If the historic maximum ineffective dose remains ineffective then a new Class I or III AAD may be initiated.

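### Being off antiarrhythmic drugs at 15 months is a reversible status at one time, but Section 8.2.2 assigns it to Kaplan-Meier and the visible text names no event or time origin

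*Combined protocol and SAP*

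**What the plan says.** Section 8.2.2 gives each additional evaluation a method tag. The AAD item reads "Proportion of subjects off all Class I or III AADs taken to treat AF/AFL/AT at 15-months (SURV". The section explains the tag: "Survival (SURV) analysis will be conducted to analyze time-to-event variables". It adds that "Subjects without events will be censored at their last known event-free time point", and that results are shown by the Kaplan-Meier product limit method. It also has a CAT tag, for subject counts and percentages.

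Section 6.2.2 (Antiarrhythmic Drug Therapy) describes how AAD status may move:

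- In the blanking period, "it is recommended that any current AAD medication be continued following the ablation procedure to aid with healing".
- Current AADs are then to be withdrawn four to six weeks after ablation, unless clinically contraindicated.
- Later use is foreseen in the sentence that begins "If the investigator feels that the subject may benefit from a Class I or III AAD during the 9-month evaluation period".

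Section 5.3.2 adds that "Intolerance is defined as unable, unwilling, or refusal to take Class I or III AADs", so some subjects may never take one.

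On data, Section 6.2.2 says that "AAD usage (start and stop date, time, frequency and dose information) will be documented for the trial" before and after the procedure. Section 6.7 lists AAD usage among the items documented at the 15-month visit (450 ± 30 days).

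**The concern.** Kaplan-Meier estimates the chance of not yet having had a first event by a given time. It needs an event, an origin and a rule for subjects who are already in the event state at the origin. The visible text gives none of these for the AAD item, so the censoring rule has no event to refer to. Even with an event supplied, a subject who takes an AAD in month 8 and is off it at month 15 is off by the label, yet has already failed on a first-use curve.

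What is at stake is a descriptive figure that may not be the quantity its label names, and that two programmers could compute differently from the same records. Section 1.1.2 says the trial's data will support a wider indication, but it does not name this item.

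**Working it through.** The documents state no expected AAD proportion, so there is no plan figure to reproduce. The mismatch between label and method follows from the text alone. The arithmetic below only shows what it can do, and its counts are assumptions.

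**Inputs from the documents.** About 100 subjects (Section 1.0). A 90-day blanking period plus 90 days of therapy consolidation puts the start of the evaluation period at day 180 (Section 3.1). Nine further months, about 270 days, end at 90 + 90 + 270 = day 450, the nominal 15-month visit.

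**Assumed counts (100 subjects, no loss to follow-up).**

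- 30 are not on an AAD after ablation. Of these, 3 start one after day 180 and are still on it at 15 months, so 27 never use one.
- 70 are on an AAD after ablation. Of these, 10 never stop and 60 stop before day 180.
- Of the 60 who stop, 7 restart after day 180 and are still on at 15 months, and x restart and are off again by then. The other 53 − x stay off.

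**Labelled quantity.** Off at 15 months = 27 + (53 − x) + x = 80, which is 80% for every x.

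**Kaplan-Meier readings.** With no loss, each equals a simple proportion.

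| Event and origin | Formula | x = 0 | x = 5 | x = 10 | x = 20 |
|---|---|---|---|---|---|
| First AAD use from day 180 | (80 − x)/100 | 80% | 75% | 70% | 60% |
| Restart or start, among the 90 off at day 180 | (80 − x)/90 | 88.9% | 83.3% | 77.8% | 66.7% |
| First stop, never-users counted as no event | 60/100 | 60% | 60% | 60% | 60% |
| First stop, among the 70 users | 60/70 | 85.7% | 85.7% | 85.7% | 85.7% |
| First stop, never-users counted as stopped at day 0 | (60 + 30)/100 | 90% | 90% | 90% | 90% |

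The readings run from 60% to 90% around a true 80%. Only the first has an exact rule: with no loss it understates by x, the subjects who used an AAD after day 180 and were off again at 15 months. The others have no fixed size or direction of error.

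**Second check, different model.** A simulated on/off process over days 181 to 450, N = 100 with 10% dropout, again with assumed rates. Each row gives the share on an AAD at day 180, then the shares starting and stopping over 270 days.

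| On / start / stop | True off | First use | Restart among those off at day 180 | Ever stopped (1 − KM) |
|---|---|---|---|---|
| 10% / 10% / 30% | 0.85 | 0.81 | 0.90 | 0.93 |
| 20% / 10% / 30% | 0.79 | 0.72 | 0.90 | 0.86 |
| 30% / 15% / 50% | 0.76 | 0.60 | 0.85 | 0.85 |
| 40% / 15% / 60% | 0.76 | 0.51 | 0.85 | 0.84 |

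The simple proportion off among subjects with known status matched the true value within 0.002 in each row. The first-use gap grows as more subjects switch status.

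**The case against.** **The definition may exist.** The list of additional data under Section 4.2, Section 8.1 and some definition tables are redacted, and the table mockups are not supplied. This stands as a limit: the missing event and origin can be claimed only of the visible text. It does not remove the point, because a first-event definition given elsewhere would still generally yield a different number from a proportion off at 15 months.

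**One sensible reading agrees with the label.** First use after day 180 returns 80% when x = 0, and no document gives any x. This also stands. The plan shows a wrong tag or a missing definition; it does not show a large error.

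**A reader might infer a far larger spread.** Counting first use from day 0 gives 27/100 = 27% in the illustration. The documents do not support that reading, because it would count as failure the early AAD use that Section 6.2.2 itself recommends. It is left out of the range.

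**A reader might extend the point to recurrence.** Single procedure success, assessed "during the 9-month period following the blanking and therapy consolidation periods after a single ablation procedure (SURV", is also under SURV. There the event is defined, and day 450 can be inferred from Section 3.1 and the visit schedule. Dating visit-detected recurrences to the visit is a general feature of Kaplan-Meier and not an error of this plan. At most, the day at which that curve is read should be stated if it is not already.

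**Kaplan-Meier handles dropout.** It does so for a defined first event. For a two-way status, the known-status denominator with the number unknown is more transparent.

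**Conclusion.** The concern holds for the AAD item. As tagged, it asks a first-event method to report a reversible status at one time, and the visible text supplies neither event nor origin. The result is generally not the labelled proportion. In the assumed 100-subject illustration, plausible readings give about 60% to 90% against a true 80%. That range rests on invented counts and cannot be read as the error this trial will make.

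The consequence is modest. Section 4.0 says that only non-powered endpoints are assessed, Section 8.2.2 rules out hypothesis tests, and Section 8.10 says that pass/fail criteria do not apply. A reader might infer that the indication expansion in Section 1.1.2 depends on this number, but the documents do not say so. It is worth correcting because the right method is already in the same section and the data are already collected.

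**What to change.** Retag the AAD item as CAT. Report the number of subjects off all Class I/III AADs at the 15-month visit, divided by the number with known AAD status in that window, and give the number with unknown status. If wanted, add an exact 95% confidence interval and bounds that set all unknowns to on, then to off. In the illustration this returns 80/100 = 80% whatever x is (exact 95% CI 70.8% to 87.3%).

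If a time-to-event summary is also wanted, name its event and origin, say how subjects on an AAD at the origin are handled, and label it as that quantity.

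The cost is wording and programming; no new data are needed. The downside is that subjects with unknown status leave the denominator. For example, with 10 of 100 unknown and 72 of 90 off, the estimate is 80%, the exact 95% CI is 70.2% to 87.7%, and the bounds are 72/100 = 72% and (72 + 10)/100 = 82%.

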## Clinical Investigation Plan

### 1.0 INTRODUCTION

This clinical investigation is intended to collect safety and effectiveness information for the TactiCath™ Contact Force Ablation Catheter, Sensor Enabled™ (TactiCath SE) for use in cardiac electrophysiological mapping and for the treatment of drug-refractory, recurrent symptomatic persistent atrial fibrillation (AF) when used in conjunction with a compatible radiofrequency (RF) generator and three-dimensional mapping system. This clinical investigation will be a post-market observational study and is intended to generate additional clinical evidence for the TactiCath SE ablation catheter for the treatment of drug refractory, symptomatic persistent atrial fibrillation in the Asia Pacific (APAC) region. Approximately one hundred (100) subjects will be enrolled at up to 15 sites in South Korea, Singapore, Hong Kong, Taiwan, India, and other Asia Pacific countries as deemed necessary. This clinical investigation is sponsored by Abbott and will be conducted in accordance with this clinical investigation plan (CIP). All investigators involved in the conduct of the clinical investigation will be qualified by education, training, or experience to perform their tasks and this training will be documented appropriately.

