### 4.0 ENDPOINTS

Only non-powered endpoints will be assessed in this trial.

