## Clinical Investigation Plan

### 5.5 Subject Withdrawal

Each enrolled subject shall remain in the clinical investigation until completion of the required follow-up period. However, a subject's participation in any clinical investigation is voluntary and the subject has the right to withdraw at any time without penalty or loss of benefit. Conceivable reasons for discontinuation may include, but not be limited to, the following:

- Death
- Voluntary withdrawal
- Lost to follow-up (described below)
- Subject's following is terminated according to **Section 3.3**

The Sponsor must be notified of the reason(s) for subject discontinuation. The site will provide this information to the Sponsor as documented on the appropriate CRF. Investigators must also report this to their respective IRB/EC as defined by their institution's procedure(s).

No additional follow-up will be required or data recorded from subjects once they are withdrawn from the clinical investigation, except for the status (deceased/alive). If a subject withdraws from the investigation due to problems related to the safety or performance of the device under investigation, they will be followed by their regular physician per their standard of care.

If for any reason, the subject has the TactiCath SE inserted into their vasculature, but no ablation was performed, and the subject will not be rescheduled to receive another ablation procedure, the subject will be followed for 30-days to assess safety and then exited from the trial.

In the event that a subject does elect to withdraw from the trial, the site should make attempts to schedule the subject for a final visit. At this final follow-up visit, the subject will undergo assessments as outlined for an unscheduled visit (**Section 6.7.1**) if the visit does not coincide with a scheduled follow-up visit.

Withdrawn subjects count towards the total enrollment at the site and will not be replaced by enrolling additional subjects.

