#### **6.7.1 Unscheduled Visits**

If a subject is seen by any physician for possible AF recurrence and/or arrhythmia associated symptoms outside of a regularly scheduled study visit and/or had an urgent care or emergency room visit regarding possible arrhythmia recurrence, these visits need to be documented as “Unscheduled Visits”, unless the visit is already documented on an Adverse Event CRF. If there is an Adverse Event associated with this visit, then an Unscheduled Visit CRF does not need to be completed.

Minimally, the following information should be documented for an unscheduled visit.

- 12-lead ECG, if performed during the visit
- Document AAD and anticoagulant usage
- Document adverse events and protocol deviations

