## Clinical Investigation Plan

### 6.7.2 Patient Reported Outcome Measures – EQ-5D-5L Questionnaires

The coordinator or designee will administer patient-reported outcome questionnaires. It is important the subject understands the meaning of all words and instructions in the questionnaires. The subject should be instructed to ask any questions about the questionnaires if further explanation is needed. Once the questionnaires are completed, the coordinator or designee will review for completeness to verify that all questions have been answered according to the directions provided.

The EuroQol Five Dimensions Questionnaire (EQ-5D-5L) patient-reported outcome measure will be collected for this trial. The EQ-5D-5L questionnaire is a standardized measure of health status that is applicable to a wide range of health conditions and treatments. It provides a simple descriptive profile and a single index value for health status that can be used in the clinical and economic evaluation of health as well as in population health surveys. EQ-5D-5L is designed for self-completion and is ideally suited for use in postal surveys, in clinics, and in face-to-face interviews and takes only a few minutes to complete. The questionnaire includes five dimensions assessing mobility, self-care, usual activities, pain/discomfort, and anxiety/depression. Each dimension is measured based on responses to 5 levels: no problems, slight problems, moderate problems, severe problems, and extreme problems. Respondents evaluate their overall health status using a visual analogue scale, which can easily be converted to quality-adjusted life years for cost utility analysis.

Note that it will not be a deviation for the EQ-5D-5L questionnaire be administered by phone. Research personnel should use the EQ-5D-5L Script for Telephone Interview questionnaire for visits conducted over the phone.

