### 8.7 Procedures for Accounting for Missing Data

Every effort will be made to collect all required data. All data available for the endpoints specified among the analysis population will be used. Missing data will not be imputed. Kaplan-Meier analysis will censor subjects withdrawn or otherwise lost-to-follow-up at last known visit.

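### EQ-5D-5L change is summarised by visit on available data, and an off-schedule exit visit does not require the questionnaire, so the mean gain may be overstated if subjects who leave do worse

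*Combined protocol and SAP*

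**What the plan says.** **Analysis.** Section 8.2.2 lists "Changes in EQ-5D-5L scores from baseline to follow-up at 3, 6, 12, and 15-months after the initial procedure (CONT"). CONT means the number of observations, mean and SD, quartiles and range. Section 8.2 says that the endpoints and additional evaluations "will be summarized descriptively based on available data or measurements in the analysis population", and Section 8.7 adds "Missing data will not be imputed". The only explicit rule for early leavers in the outcome analyses beyond the safety endpoint is censoring, and it applies to the Kaplan-Meier analyses.

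**Collection at exit.** Section 5.5 asks sites to try to arrange a final visit, at which "the subject will undergo assessments as outlined for an unscheduled visit", provided it does not coincide with a scheduled one. Section 6.7.1 introduces that list with "Minimally, the following information should be documented for an unscheduled visit". It covers the ECG if one was done, antiarrhythmic and anticoagulant use, adverse events and deviations, and does not name EQ-5D-5L. After withdrawal only vital status is recorded, and withdrawn subjects are not replaced.

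**Collection otherwise.** Section 6.7 and Table 2 schedule EQ-5D-5L at 3, 6, 12 and 15 months. Section 6.7.2 states that "it will not be a deviation for the EQ-5D-5L questionnaire be administered by phone".

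**Setting.** Section 1.0: "Approximately one hundred (100) subjects will be enrolled at up to 15 sites". Section 4.0: "Only non-powered endpoints will be assessed in this trial". The readable text gives no dropout rate and no EQ-5D-5L effect or SD. Sections 8.1 and 8.3 cannot be read in the public copy, and the table mock-ups that Section 8.2.2 mentions are not included.

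**The concern.** Each visit mean is taken over whoever has a score at that visit. If loss is related to how subjects fare, the 12- and 15-month means describe a selected group, and part of any trend from 3 to 15 months reflects who remains. With a single arm, no comparison group offsets the selection.

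EQ-5D-5L is the only patient-reported outcome that the readable plan names. Section 1.1.1 describes the study as primarily about effectiveness, and Section 1.1.2 says its data will support a wider indication. With no hypothesis test, the reported mean is itself the result. Loss linked to outcome is plausible, since Section 5.5 foresees withdrawal over problems with the device. A score not taken at exit cannot be recovered afterwards.

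**Working it through.** The plan has no figure of its own to reproduce here. Every dropout rate, effect, SD and correlation below is an assumption.

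**1. What a leaver contributes.** A subject with 3- and 6-month scores who withdraws at day 250 enters the 3- and 6-month means and neither later mean. The earlier scores inform nothing after month 6.

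**2. When an exit is off-schedule.** Table 2 gives windows of 91±21, 181±30, 365±30 and 450±30 days, that is 70-112, 151-211, 335-395 and 420-480. Exits before day 70, or on days 113-150, 212-334 or 396-419, fall outside every window. An off-schedule exit is therefore not a rare corner case.

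**3. Relative size.** Let p be the share missing at a visit, G the stayers' mean gain and rG the leavers'.

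- Available-case mean = G.
- All-subject mean = (1−p)G + p·rG = G[1 − p(1−r)].
- Relative overstatement = 1/(1 − p(1−r)) − 1.

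| p | r = 0 | r = 0.5 | r = 1 |
|---|---|---|---|
| 5% | 5% | 3% | 0 |
| 10% | 1/0.90 − 1 = 11% | 1/0.95 − 1 = 5% | 0 |
| 15% | 18% | 8% | 0 |
| 20% | 1/0.80 − 1 = 25% | 1/0.90 − 1 = 11% | 0 |

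If r exceeds 1 the sign reverses and the gain is understated.

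**4. Absolute size.** Bias = p × (stayers' mean change − leavers' mean change). With a gap of 0.10 index units it is 0.10 × 0.10 = 0.010 at 10% missing and 0.20 × 0.10 = 0.020 at 20%. With a gap of −0.05 at 20% it is −0.010.

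**5. Simulation, dropout driven by the last observed score.** Assumptions: n = 100, four visits, mean change 0.06, SD 0.15, within-subject correlation 0.6, and logistic dropout with slope 4 or 8 per index unit. Absolute bias = percentage × 0.06. Standard error = 0.15/√(subjects remaining).

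| Dropout | Overstatement at month 15 (slope 4 / 8) | Absolute bias | Standard error |
|---|---|---|---|
| 5% | 4.5% / 8.9% | 0.003 / 0.005 | 0.15/√95 = 0.015 |
| 10% | 8.7% / 18.2% | 0.005 / 0.011 | 0.15/√90 = 0.016 |
| 15% | 13.8% / 24.9% | 0.008 / 0.015 | 0.15/√85 = 0.016 |
| 20% | 17.8% / 33.1% | 0.011 / 0.020 | 0.15/√80 = 0.017 |

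Only the steepest slope at 20% dropout exceeds one standard error. A repeated-measures likelihood estimate on the same data was within about 1% of the truth. That is expected, because this dropout mechanism is missing at random, the condition under which such a model is valid.

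**6. Simulation, three mechanisms.** Assumptions: n = 100, SD 0.20, correlation 0.6, about 15% missing, standard error 0.20/√85 = 0.022.

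- Missingness unrelated to outcome: bias 0.000.
- Dependent on an earlier observed score: 0.15 × 0.105 = +0.016.
- Dependent on the unseen score: 0.15 × 0.177 = +0.027.

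The third case exceeds one standard error, and a missing-at-random model alone would not fully repair it.

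**The case against.** A reader might infer that the plan overstates the gain as a matter of fact. The documents do not support that. They give no dropout rate and nothing showing that leavers do worse. Section 5.5 expects subjects to stay to the end of follow-up, and its list of discontinuation reasons, which is not exhaustive, does not name recurrence. The direction is therefore conditional.

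Two further readings are too strong:

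- **That no EQ-5D-5L is taken at exit.** A final visit that coincides with the 3-, 6-, 12- or 15-month visit collects it, and the Section 6.7.1 list is a minimum.
- **That only clinic attenders count.** Telephone administration is allowed, and Section 5.5 lets a subject who misses a visit return, so the set of contributors need not only shrink.

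It is also fair to say that n per visit is already planned under CONT, that the slopes in the simulation are chosen values (odds of dropout rise by exp(4 × 0.15) = 1.8 or exp(8 × 0.15) = 3.3 per SD of worse change), and that percentages make small index amounts look large. A mixed model omits subjects with only a baseline score. Subjects lost to follow-up may have no exit visit. EQ-5D-5L is additional data in a study with no test and no pass/fail criterion (Section 8.10), and the unseen mock-ups may hold more.

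All of this stands and limits the point. It does not close the gap: the readable plan still drops a leaver from later means, and does not ask for a score at an off-schedule exit.

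**Conclusion.** The point holds in conditional form. By-visit means on available data, without imputation, describe subjects who still have a score. They represent all treated subjects only if loss is unrelated to EQ-5D-5L change.

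If leavers have half or none of the stayers' gain, the overstatement is about 5-11% at 10% loss and 11-25% at 20%. On an assumed mean change of 0.06 and SD of 0.15, the simulated bias at 10-20% dropout is about 0.005-0.020, mostly at or below one standard error (0.016-0.017). These figures illustrate scale and are not predictions for this study.

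Severity is low, since the effect falls on a reported descriptive mean and not on a decision. The reason to act is that the missing exit score is cheap to collect and cannot be obtained later.

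**What to change.** 1. **Sections 5.5 and 6.7.1.** Add EQ-5D-5L to the final visit of a withdrawing subject, in person or with the existing telephone script. Assign the score to the nearest scheduled visit by a stated window rule. Midpoints between target days would serve: (91+181)/2 = 136, (181+365)/2 = 273 and (365+450)/2 = 407.5. The rule should also cover exits before day 70 and say which score counts if that visit already has one.
2. **Section 8.2.2.** Keep the by-visit summaries. Add a repeated-measures likelihood estimate of mean change at each visit with 95% intervals (visit as factor, baseline score as covariate, unstructured covariance). Report baseline EQ-5D-5L for subjects observed and missing at each visit.
3. **Section 8.7.** Because the model assumes missing at random and omits subjects with a baseline score only, add one simple sensitivity analysis that gives missing subjects no gain or a worse score, and state how deaths are handled. For example, with 20% missing and an observed mean of 0.06, assuming no gain gives 0.80 × 0.06 = 0.048.
4. **Section 6.1.** Correct the cross-reference for EQ-5D-5L, which points to 6.7.1 (unscheduled visits) while the follow-up visits point to 6.7.2.

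The cost is a few minutes per withdrawing subject, one standard model and one extra table. The reported gain may come out slightly smaller.
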